### **7.3. Lost to Follow-up**

Participants will be considered lost to follow-up if they repeatedly fail to return for scheduled visits and are unable to be contacted by the trial site personnel. The following actions must be taken if a participant fails to return to the site for a required trial visit:

- Trial site personnel must attempt to contact the participant and reschedule the missed visit as soon as possible and counsel the participant on the importance of maintaining

the assigned visit schedule and ascertain whether or not the participant wishes to and/or should continue in the trial.

- Before a participant is deemed lost to follow-up, the investigator or designee must make every effort to regain contact with the participant (where possible, 3 telephone calls, and a certified letter to the participant's last known mailing address or local equivalent methods). These contact attempts should be documented in the participant's medical record.

Participants who continue to be unreachable will be considered to have withdrawn from the trial.

## 8. TRIAL ASSESSMENTS AND PROCEDURES

The timing and frequency of trial procedures are provided in the Schedule of Assessments ([Section 1.3](#)). Protocol waivers or exemptions are not allowed.

At each time point during the trial, efficacy and health economics assessments should be completed before safety assessments, and every effort should be made to complete the PDSS as the first assessment. The preferred order of assessment will be specified in the Operations Manual.

Immediate safety concerns should be discussed with the medical monitor immediately upon occurrence or awareness to determine if the participant should continue or discontinue IMP.

Adherence to the trial design requirements, including those specified in the Schedule of Assessments, is essential and required for trial conduct.

All screening evaluations must be completed and reviewed to confirm that potential participants meet all eligibility criteria. The investigator will maintain a screening log to record details of all participants who are screened and to confirm eligibility or record reasons for screening failure, as applicable.

The MINI for Psychotic Disorders ([Sheehan et al, 1998](#); [Sheehan et al, 1997](#)) will be conducted at the Screening Visit to confirm the participant's diagnosis of panic disorder and to rule out exclusionary comorbid psychiatric diagnoses.

### 8.1. Efficacy Assessments

Trained and qualified (details provided in the rater training vendor plan or manual) clinicians should administer the efficacy assessments and the number of raters should be kept to a minimum. All efforts should be made to ensure the same clinician administers the scales for a given participant throughout the trial.

All efficacy assessments will be completed using an approved electronic data capture system.

Non-BZD sleep aids are not permitted within 12 hours of administration of clinician-administered scales (see [Section 6.7](#)).

The timing and frequency of efficacy assessments are provided in the Schedule of Assessments ([Section 1.3](#)).

#### 8.1.1. Panic Attack Frequency

Panic attack frequency will be assessed using an eDiary that will be completed by participants each day. Participants will record the presence/absence of panic attacks along with associated symptoms for a given day with a recall time of immediate to end of day on that same day. For each panic attack, reporting the presence or absence of each symptom referenced in the DSM-5-TR criteria (see [Section 4.1](#)) will be recorded in the eDiary. Participants will train on eDiary use at the Screening Visit and will start recording their daily frequency of panic attacks; participants must complete a minimum of 11 eDiary day entries, including days free of panic attacks, in the 14 days preceding the Baseline Visit. The panic attack frequency recorded for the 14 days prior to randomization and dosing will be used as the baseline. During the double-blind

randomized treatment period, the panic attack frequency per each 2-week period will be the basis of the repeated measure assessments.

### **8.1.2. Panic Disorder Severity Scale**

The PDSS ([Shear et al, 1997](#)) is a 7-item, clinician-administered measure of panic disorder severity that covers multiple dimensions of the disorder and has become a widely used standard measure. The first 5 items of the PDSS assess the core DSM-5-TR symptoms of panic disorder, and 2 additional items assess impairment in social and occupational functioning. Each item is scored on a 0 to 4 scale for a total of 28 points.

### **8.1.3. Clinical Global Impression-Severity of Symptoms Scale**

The global severity of panic disorder symptoms for each participant will be rated using the CGI-S ([Guy, 1976](#)). To perform this assessment, the investigator (or designee) will answer the following question: “Considering your total clinical experience with this particular population, how ill with panic disorder symptoms is the participant at this time?” Response choices are 0=not assessed; 1=normal, not at all ill; 2=borderline ill; 3=mildly ill; 4=moderately ill; 5=markedly ill; 6=severely ill; and 7=among the most extremely ill participants.

## **8.2. Safety Assessments**

The timing and frequency of safety assessments are provided in the Schedule of Assessments ([Section 1.3](#)).

### **8.2.1. Height and Weight**

Height will be measured with a stadiometer, measuring stick, or tape.

The following guidelines will aid in the standardization of body weight measurements:

- Scales should be calibrated and reliable; scales should be at zero just prior to each participant’s weigh-in session
- A participant should void prior to being weighed, if possible, and be minimally clothed (ie, no shoes or heavy overgarments)
- Weight should be recorded before a participant’s meal and at approximately the same time at each required visit

### **8.2.2. Physical and Neurological Examinations**

A full physical examination will include a review of the following body systems: head, ears, eyes, nose, mouth, skin, heart and lungs, lymph nodes, gastrointestinal, and musculoskeletal systems.

A limited physical examination will include evaluation of cardiovascular, pulmonary, and gastrointestinal systems.

A full neurological examination will include an assessment of the participant’s mental status (level of consciousness, orientation, speech, memory, etc), cranial nerves, motor (muscle

appearance, tone, strength and reflexes), sensation (including Romberg sign), coordination, and gait.

The investigator (or designee) is responsible for performing the physical and neurological examinations. If the appointed designee is to perform these examinations, he or she must be permitted by local regulations and his or her name must be included on the delegation of authority log. Whenever possible, the same individual should perform all physical and neurological examinations.

The investigator must review the physical and neurological examination findings and document any clinically significant condition present at the post-treatment physical and neurological examinations that was not present at the baseline examination as an AE. These clinically significant findings should be followed to a satisfactory conclusion.

### **8.2.3. Vital Sign Measurements**

Vital signs include systolic and diastolic blood pressures, heart rate, respiratory rate, and body temperature. At the Screening Visit, triplicate blood pressure and heart rate measurements will be obtained after the participant has been supine and at rest for at least 3 minutes. Measurements will be obtained at approximately 1-minute intervals at the time points indicated in the Schedule of Assessments ([Section 1.3](#)). Duplicate supine heart rate and blood pressure measurements will be taken at all other time points. The values will be individually recorded, and the values will be averaged by the sponsor for all time point assessments following confirmation of eligibility. For determination of eligibility, the average of the last 2 values will be used (see [Section 5.2](#)). The supine heart rate and blood pressure measurements will be followed by a single measurement after approximately 2 minutes in a standing position to allow for orthostatic assessments. Additional details are provided in the Operations Manual.

### **8.2.4. Electrocardiograms**

Electrocardiogram recordings will be obtained after the participant has been supine and at rest for approximately 3 minutes. Additional 12-lead ECGs may be obtained at the investigator's discretion and should always be obtained in the event of an early termination. The ECG results will be evaluated at the investigational site to determine the participant's eligibility and to monitor safety during the trial. The principal investigator (or qualified designee) will review, sign, and date each ECG reading, noting whether or not any abnormal results are of clinical significance. The ECG will be repeated if any results are considered to be clinically significant. Any clinically significant changes occurring during the trial will be recorded in the AE section of the eCRF. A central ECG service will be used for reading all ECGs in order to standardize interpretations for the safety analysis. Additional guidance on collection of ECGs will be provided in the Operations Manual.

At Screening, triplicate 12-lead ECGs are required to assess participant eligibility. A triplicate set of ECGs is 3 consecutive ECGs collected 1 to 2 minutes apart over a 5-minute period. If, during screening, according to the investigator's judgment, any abnormal ECG finding is deemed medically significant (impacting the safety of the participant or the interpretation of the trial results) or meets an exclusion criterion (see [Section 5.2](#)), the participant should be excluded from

the trial. The central ECG service will provide the QTcF corrections and average of the 3 ECGs performed to determine eligibility.

At all other specified time points in the Schedule of Assessments ([Section 1.3](#)) where an ECG recording must be performed, only a single ECG is required.

Exclusion criteria for screening do not apply as mandatory discontinuation criteria for participants who are already randomized. A repeat ECG should be performed in case of any clinically significant abnormality that is identified in a randomized participant during the treatment period and, in these cases, the medical monitor should be consulted on the appropriateness of the participant continuing in the trial.

### **8.2.5. Clinical Safety Laboratory Assessments**

See [Section 10.2](#) for the list of clinical laboratory tests to be performed and the Schedule of Assessments ([Section 1.3](#)) for the timing and frequency.

The investigator must review the laboratory report, document this review, and record any clinically relevant changes occurring during the trial as an AE. The laboratory reports must be filed with the source documents.

All laboratory tests with values considered clinically significantly abnormal during participation in the trial should be repeated until the values return to normal or baseline or are no longer considered clinically significant by the investigator or medical monitor. If clinically significant values do not return to normal/baseline within a period of time judged reasonable by the investigator, the etiology should be identified and the medical monitor notified.

All protocol-required laboratory tests, as defined in [Section 10.2](#), must be conducted in accordance with the laboratory manual and the Schedule of Assessments.

### **8.2.6. Suicidal Ideation and Behavior Risk Monitoring**

Suicidality will be monitored during the trial using the C-SSRS. This semi-structured interview was originally developed to evaluate the link between antidepressants and suicidal behavior and ideation in youth and adverse events from pediatric clinical trials ([Posner et al, 2011](#)). It was designed to quantify the severity of suicidal ideation and behavior. Trial personnel administering the C-SSRS must have completed the appropriate training and have valid certification. Access to training on the scale will be provided by the sponsor or designee.

This trial will use the “Baseline/Screening” and “Since Last Visit” versions of the scale. The “Baseline/Screening” version will be completed for all participants at Screening to determine eligibility. The exclusion criteria based on the C-SSRS are provided in [Section 5.2](#).

The “Since Last Visit” C-SSRS form will be completed after the Screening visit. The investigator will review the results of the “Since Last Visit” C-SSRS during the trial to determine whether it is safe for the participant to continue in the trial. If a participant has any “YES” answers on the C-SSRS for the suicidal ideation or suicidal behavior items, the investigator will evaluate whether a risk assessment by a qualified mental health professional (or the investigator alone if the investigator is a qualified mental health professional) is needed and discuss with the medical monitor whether the participant should continue in or be discontinued from the trial.

### **8.2.7. Penn Physician's Withdrawal Checklist**

The PWC is a 20-item scale to measure discontinuation symptoms after stopping a medication for anxiety disorders (Rickels et al, 2008; Rickels et al, 1990). All 20 items are rated on a 4-point numeric-rating scale ranging from 0 (not present), 1 (mild), 2 (moderate), to 3 (severe). A total score, ranging 0 to 60, can be calculated in addition to the individual scores for each item. Lower scores indicate less severity in discontinuation symptoms.

## **8.3. Adverse Events, Serious Adverse Events, and Other Safety Reporting**

The definitions of AEs and SAEs can be found in [Section 10.3](#). Definitions of AESIs are provided in [Section 8.3.7](#).

Adverse events will be reported by the participant (or, when appropriate, by a caregiver, surrogate, or the participant's legally authorized representative). The investigator and any qualified designees are responsible for detecting, documenting, and recording events that meet the definition of an AE, SAE, or AESI and remain responsible for following up AESIs and AEs that are serious, considered related to the IMP or trial procedures, or that caused the participant to discontinue IMP (see [Section 7.1](#)).

Further details about AE recording and follow-up are provided in [Section 10.3](#).

### **8.3.1. Time Period and Frequency for Collecting AE and SAE/AESI Information**

All AEs and SAEs/AESIs will be recorded from the first dose of IMP until follow-up contact at the time points specified in the Schedule of Assessments ([Section 1.3](#)).

Medical occurrences that begin before the start of IMP dosing but after obtaining informed consent will be recorded as medical and/or psychiatric history.

All SAEs/AESIs will be recorded and reported to the sponsor or designee immediately and under no circumstance should this exceed 24 hours, as indicated in [Section 10.3](#). The investigator will submit any updated SAE/AESI data to the sponsor or designee within 24 hours of it being available.

Investigators are not obligated to actively seek AEs, AESIs, or SAEs after conclusion of the trial participation. However, if the investigator learns of any SAE, including a death, at any time after a participant has been discharged from the trial, and considers the event to be related to the IMP or trial participation, the investigator must promptly notify the sponsor.

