Trial Periods/Phases	Screening (up to 4 weeks) a			Treatment								Follow-up (4 weeks)		
				Titration (2 weeks)		Maintenance (12 weeks)								
Visit/Contact	Screening/ Visit 1	Baseline/ Visit 2		Telephone Contact	Visit 3	Telephone Contact	Visit 4	Telephone Contact	Visit 5	Telephone Contact	Visit 6	Visit 7 (Telephone)	Visit 8 (Telephone)	Visit 9
Day	-28 to -2	-1	1	7	14	28	42	56	70	84	98/ET b	101	105	131
Window				±3 days								±1 day	±3 days	
Screening only laboratory tests: hepatitis B, C, HIV, and serum FSH p,q	X													
PK blood sample f					X		X		X		X			
Blood sample for future biospecimen research s		X												
Other														
IMP dispensing		X t			X		X		X					
Dosing starts			X											

Abbreviations: BID=twice daily; CGI-S=Clinical Global Impression-Severity of Symptoms Scale; C-SSRS=Columbia-Suicide Severity Rating Scale; ECG=electrocardiogram; EQ-5D-5L=European Quality of Life; ET=early termination; FSH=follicle-stimulating hormone; HAM-A=Hamilton Anxiety Scale; HIV=human immunodeficiency virus; IMP=investigational medicinal product; MINI=Mini International Neuropsychiatric Interview; PCR=polymerase chain reaction; PDSS=Panic Disorder Severity Scale; PK=pharmacokinetic; PWC=Physician's Withdrawal Checklist; SDS=Sheehan Disability Scale.

a Participants will enter a Screening Period of at least 14 days and up to 28 days.

b If a participant discontinues early, the participant should follow the safety follow-up procedures (Visits 7-9).

c Review of inclusion/exclusion criteria includes review of eDiary data to assess panic attack frequency.

d Inclusion/exclusion criteria will be assessed at Baseline to ensure ongoing participant eligibility, with the exception of age or assessments that are only scheduled during Screening (eg, height for body mass index calculation).

e Medical occurrences that begin before the start of dosing with IMP but after obtaining informed consent should be collected as medical and/or psychiatric history.

f A breathalyzer alcohol test is required at the Screening Visit and at Baseline. The alcohol test (breathalyzer or blood/urine) can be conducted at any time during the trial at the discretion of the investigator.

g The eDiary will be collected through Visit 8 (Day 105). Physical devices will be collected at the last in-person visit.

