h Full physical and neurological examinations should be completed at Screening. Limited examinations (cardiovascular, pulmonary, and gastrointestinal) should be completed at all other specified time points. Symptom-driven physical and/or neurological examinations may be done at any time during the trial at the investigator's discretion.

- i 12-lead ECG assessments will be performed after the participant has been at rest for approximately 3 minutes. At Screening, the average of 3 consecutive ECGs collected 1 to 2 minutes apart will be used to determine participant eligibility; at Baseline, only 1 reading is required for determination of eligibility. Single ECGs will be obtained at all other time points. Additional ECGs can be performed at the investigator's discretion (eg, if abnormalities are noted).
- j Blood pressure and heart rate assessments should be performed in order to confirm eligibility (see Exclusion Criterion in [Section 5.2](#)). Triplicate supine heart rate and blood pressure measurements should be taken at approximately 1-minute intervals at the Screening Visit. Duplicate supine heart rate and blood pressure measurements will be taken at all other time points. The supine heart rate and blood pressure measurements will be followed by a single measurement after approximately 2 minutes in a standing position to allow for orthostatic assessments. Additional time points can be added at the investigator's discretion (eg, if abnormalities are noted). Further details are provided in [Section 8.2.3](#) and in the Operations Manual.
- k Visit 6 will be considered the baseline assessment for the PWC.
- l Prior and concomitant medications, including cannabis products, should be recorded from Screening through the participant's last visit/contact.
- m Adverse events (serious and nonserious) should be recorded from the first dose of IMP on Day 1 (eg, the day after Baseline) through the participant's last visit/contact.
- n For women of childbearing potential only. Pregnancy tests can be performed at any time during the trial at the discretion of the investigator if pregnancy is suspected. Any urine pregnancy tests that are positive must be confirmed using a serum test.
- o Additional urine drug screening can be conducted at any time during the trial at the discretion of the investigator.

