### **6.7.2. Prohibited Therapy**

Participants are required to discontinue use of prohibited medications in accordance with predefined washout periods, as shown in [Table 5](#).

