**Table 5: Prohibited Prior Medications**

Prohibited Prior Medications	Washouta (if applicable)
Moderate or strong inducers of CYP3A4 metabolism (see Section 10.7 )	5 weeks
Moderate or strong inhibitors of CYP3A4, including Paxlovid (see Section 10.7 )	14 days or 5 half-lives, whichever is longer
P-gp substrates with a narrow therapeutic index (eg, digoxin, dabigatran)	14 days
BCRP substrate rosuvastatin	5 days
All psychoactive substances other than antidepressants (unless otherwise noted) including but not limited to: 
 
• Opiates
 
• Anxiolytics (eg, benzodiazepines, non-benzodiazepine anxiolytics)
 
• Beta receptor antagonists used for any indication
 
• Antiseizure/neuropathic pain medications used for any indication (eg, gabapentin, pregabalin, topiramate, phenytoin, phenobarbital)
 
• Hypnotics 
 
○ Sleep medications (eg, zolpidem, zaleplon, eszopiclone, trazodone, and suvorexant or other orexin receptor antagonists) are permitted if medically prescribed at doses labeled for insomnia and used no more than 3 times per week
 
 
 
• Mood stabilizers (eg, lithium, divalproex, carbamazepine, lamotrigine)
 
• Stimulants (eg, amphetamine, methylphenidate, modafinil)
 
• Antipsychotics
 
	14 days
Antidepressants	14 days, except for fluoxetine and Symbyax, which require a washout of 28 days
D2/3 agonist (eg, pramipexole)	14 days or 5 half-lives, whichever is longer
Any investigational agent	60 days

Abbreviations: BCRP=breast cancer resistance protein; CYP=cytochrome P450; D2/3=dopamine D2/D3 receptor agonist; ICF=informed consent form; P-gp=P-glycoprotein.

a The required washout duration is based on the period prior to the Baseline Visit. Once the participant signs the ICF, the participant has up to 28 days prior to the Baseline Visit to washout. If the participant happened to washout prior to the Screening Visit for their own reasons and out of their own will, this is acceptable and must be documented in the medical records. Following consultation with the medical monitor, the Screening Period may be extended if needed to accommodate a washout duration that is longer than 28 days.

The concomitant medications that are prohibited during the trial are listed in [Table 6](#).

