### 10.3. Adverse Events: Definitions and Procedures for Recording, Evaluating, Follow-up, and Reporting

#### 10.3.1. Definition of AE

**Table 9: Definition of AE**

AE Definition

 
An AE is any untoward medical occurrence in a patient or clinical trial participant, temporally associated with the use of trial intervention, whether or not considered related to the trial intervention.
 
NOTE: Signs and symptoms and/or abnormal laboratory test result indicating a common underlying pathology/diagnosis should be reported as a single AE.
 

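### Events between consent and first dose are filed as history, so a serious reaction to required washout has no clear 24-hour sponsor report and no causality judgement against the washout

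*Protocol*

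**What the plan says.** **When recording starts.** Protocol 8.3.1 records AEs, SAEs and AESIs from the first dose. Of earlier events it says: "Medical occurrences that begin before the start of IMP dosing but after obtaining informed consent will be recorded as medical and/or psychiatric history". Table 1 repeats this. Footnote e reads "Medical occurrences that begin before the start of dosing with IMP but after obtaining informed consent should be collected as medical and/or psychiatric history" and footnote m reads "Adverse events (serious and nonserious) should be recorded from the first dose of IMP on Day 1". The schedule in SAP 9.1 carries the same two footnotes. None of these places makes an exception for serious or procedure-related events.

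**Washout.** Protocol 6.7.2 states: "Participants are required to discontinue use of prohibited medications in accordance with predefined washout periods". Table 5 covers benzodiazepines and other anxiolytics, antidepressants, opiates, antiseizure drugs and more. On timing, footnote a says: "Once the participant signs the ICF, the participant has up to 28 days prior to the Baseline Visit to washout". It also accepts washout completed earlier: "If the participant happened to washout prior to the Screening Visit for their own reasons and out of their own will, this is acceptable".

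**What counts as an AE or SAE.** Table 9 defines an AE as an occurrence "temporally associated with the use of trial intervention, whether or not considered related to the trial intervention". Section 6 defines trial intervention by the products to be given, which does not include stopping a prior drug. Section 10.3.2 adds that an event outside the AE definition cannot be an SAE, however serious. Table 13 obliges the investigator to judge the relationship to the trial intervention, with both answer categories worded for the IMP. Yet Protocol 8.3 says investigators "remain responsible for following up AESIs and AEs that are serious, considered related to the IMP or trial procedures", so the protocol recognises that a trial procedure can cause harm.

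**The concern.** The trial asks participants to stop drugs whose withdrawal can itself be harmful. Protocol 2.2.1 cites the boxed warning for benzodiazepines, which names withdrawal reactions. The protocol monitors withdrawal after darigabat with the PWC and telephone contacts at about 3 and 7 days. The PWC has its baseline at Visit 6, so it does not reach the washout before dosing.

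Suppose a participant is hospitalised during a washout that the protocol required. The stated rule makes this medical history. It triggers neither the 24-hour report nor the question of whether washout was the cause. What is at stake is participant safety and the sponsor's ability to notice a pattern across sites. A participant harmed in washout may also never be randomized, and that is where the data requirements are thinnest.

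**Working it through.** The plan states no figure on this point. The check is to follow one event through the rules, then see what other text would catch it.

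**The event.** A serious reaction, such as an admission, starts after consent and before Day 1 during a Table 5 washout.

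1. Recording: before first dose, so history (8.3.1; Table 1 footnotes e and m; SAP 9.1 footnotes e and m).
2. AE status: no trial intervention has been used, so Table 9 is not met on its wording.
3. SAE status: not an AE, so not an SAE (10.3.2), even if a Table 11 seriousness criterion is met.
4. Reporting: the 24-hour rule in 8.3.1 applies to SAEs and AESIs, so it is not clearly triggered.
5. Causality: Table 13 asks only about the trial intervention and only for AEs, SAEs and AESIs. No judgement against washout is required.

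**Can washout fall in this window?** Screening lasts 14 to 28 days (4.1.1). Table 5 asks for 14 days for benzodiazepines and most antidepressants, and 28 days for fluoxetine and Symbyax. Both fit wholly after consent. CYP3A4 inducers need 5 weeks: 5 × 7 = 35 days, which exceeds ordinary screening by 35 − 28 = 7 days and needs an extension agreed with the medical monitor. Table 1 shows no scheduled contact between Visit 1 (as early as Day -28) and Visit 2 (Day -1), a gap of up to 27 days.

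**Other text that might catch the event.**

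| Place | What it gives | What it leaves open |
|---|---|---|
| Protocol 8 | Immediate contact with the medical monitor | Its stated purpose is the decision on IMP; no report or causality |
| Protocol 8.2.4, 8.2.5 | ECG and laboratory changes of clinical importance during the trial go to the AE record; both tests are done at Baseline | Only those findings; conflicts with 8.3.1 before dosing |
| Protocol 8.2.6, 8.3.7 | C-SSRS at Baseline; certain answers are AESIs | Suicidality only; AESI recording still starts at first dose, and SAP 3.2.3 places the follow-up form after Baseline |
| Protocol 8.3.1, last paragraph | Notice of SAEs related to trial participation | Only if learned of after discharge; prompt, with no 24-hour limit |
| Protocol 10.1.1 | Notice of significant safety findings to the IRB/IEC | Not a sponsor report |
| Table 10 | AE if the condition worsens, or is newly detected, after dosing | Nothing for someone never dosed |
| Protocol 5.4; SAP 5.6 | Screen-failure details, and reasons tabulated | No safety item named in the minimum data set |
| SAP 3.2.1, 5.17.1 | Wording leaves room for pre-dose AE records, and all AEs are listed | Only if a site enters the event as an AE, against 8.3.1 |

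**Listings.** SAP 5.1 promises listings of all data from consented participants, including screen failures. SAP 5.7 lists history for the ITT set, and SAP 9.4 prepares listings for randomized participants. Whether a screen failure's event would be listed is unsettled.

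**The case against.** The strongest reply is that this is a deliberate and consistent choice. The same rule stands in 8.3.1, Table 1 and SAP 9.1, and the documents set no other standard for pre-dose events. Several routes would bring a serious case to someone's attention. Exclusion criterion 12 provides for contact with the medical monitor over abnormal safety findings, rescreening needs consultation with the sponsor, and washout beyond 28 days needs the medical monitor. The Operations Manual, CRF Completion Guidelines and eCRF were not available and might contain a pre-dose reporting rule. Enrolment has closed, so a change in collection cannot help this trial.

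Most of this stands as a limit on the point. The routes make silence less likely. None of them, however, requires the 24-hour report together with a judgement on washout, and the rule's consistency is why the gap is not closed elsewhere. The contact gap of up to 27 days bears on detection, and a reporting rule does not shorten it.

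Three stronger readings are tempting, and the documents support none of them:

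- **That such events are lost, or can never reach an AE output.** They are recorded as history; ECG and laboratory findings may go to the AE record; and the SAP would list a pre-dose event entered as an AE.
- **That the length of the window measures risk.** It is calendar time that applies to everyone, including those with nothing to wash out.
- **That the efficacy or safety comparison is affected.** The events precede dosing, and the TEAE window properly starts at first dose.

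**Conclusion.** The point holds as a participant-safety gap and as a cheap improvement. On the two documents, a serious reaction to required washout between consent and first dose has no clear 24-hour sponsor report and no required causality assessment against the washout. Cover is partial, and part of it (8.2.4 and 8.2.5) conflicts with 8.3.1.

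The frequency cannot be estimated: the documents give neither the number washing out after consent nor a reaction rate. Only the window can be stated, at 14 to 28 days, or 35 days in the extended case. The point concerns only participants who wash out after consent. It rests on reading Table 9 and 10.3.2 literally, and on no unseen manual supplying the rule. It does not bear on the treatment comparison.

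**What to change.** **Protocol, for reuse of the design.** Add to 8.3.1, and to footnotes e and m of both schedules (Table 1 and SAP 9.1):

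> *Notwithstanding Table 9 and 10.3.2, from consent to first dose, any event meeting the Table 11 seriousness criteria and judged by the investigator related to a protocol-required procedure, including washout, is reported to the sponsor as an SAE within 24 hours, including for screen failures.*

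Add to Table 13 a related / not related judgement to trial procedures for these events; without it the new sentence has no causality category to use. Align 8.2.4 and 8.2.5 with 8.3.1 so that it is clear where a Baseline ECG or laboratory finding goes. Leave the general AE and SAE definitions otherwise as they are.

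**SAP.** List these events for All Screened Participants, a set already defined in Table 14, as a stated exception to the randomized-only rule in 9.4. TEAE tables stay unchanged.

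**This trial.** List history events with onset between consent and first dose for all screened participants, where collected, with a short medical review to pick out the serious ones. The review is needed because neither document describes a seriousness or relatedness field for history. SAP 6 provides for documenting such a departure in the study report.

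**Cost.** For reuse: a few extra SAE reports from screening, a small change to the form and site training, and one listing. For this trial: one listing and the review. Screen-failure history may be incomplete, because the 5.4 minimum does not ask for it.
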